Statistical Analysis Plan

Compound Name:	TEW-7197
Protocol no:	MP-VAC-105(version 1.2)
IRB No:	18-0122
NCT Number	NCT03704675
Study Title:	A randomized, open, cross-over design clinical trial to investigate the safety, tolerability, and pharmacokinetics of TEW-7197 after a single oral administration of TEW-7197 200 mg under fed or fasting conditions in healthy male subjects

Statistical analysis	
• Demographic and baseline characteristics By TEW-7197 sequence, descriptive statistics (number of subjects, mean, standard deviation, range, minimum, median, maximum) were tabulated for demographic information such as age and sex and physical measurement/baseline characteristics such as height, weight, body mass index, drinking level and blood donation, and frequency and percentage were tabulated for categorical data. In order to confirm validity of randomization and subsequent analysis, statistical significance was assessed using an independent sample T test or Mann-Whitney test for continuous variables by sequence.• Pharmacokinetic analysis After calculating pharmacokinetic parameters by patient, descriptive statistics such as mean, standard deviation and CV% were presented by dose group. Descriptive statistics were presented for mean, standard deviation and CV% by treatment (fed/fasting), and the point estimate and 90% confidence interval of the mean difference between treatments were estimated by using log-transformed C_{max} and AUC_t.• Safety evaluation For adverse events and adverse drug reactions that occurred in this study, frequency (number of subjects), percentage and number of events were presented according to SOC and PT by dose group and treatment. Frequency (number of subjects), percentage and number of events were also presented for adverse events and adverse drug reactions according to SOC and PT by severity. Chi-square test or McNemar's test was used to evaluate a statistical significance between treatments. For vital signs, physical examination, 12-lead ECG, echocardiography and each item of clinical laboratory evaluations, descriptive statistics (number of subjects, mean
----------------------	--

	standard deviation, minimum, median, maximum and change from baseline (difference, change rate)) were tabulated by each measurement time, and for categorical data, frequency and percentage were tabulated. Concomitant medication was presented with lists.
--	---

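### Does the SAP pool fed and fasting data in the vital-sign, physical examination, ECG, echocardiography and laboratory summaries by naming only measurement time as their grouping?

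*Combined protocol and SAP*

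**What the plan says.** The statistical text is a single table cell with short paragraphs on demographics, pharmacokinetics and safety. The title describes a randomized, open cross-over study "after a single oral administration of TEW-7197 200 mg under fed or fasting conditions".

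The grouping factor varies by paragraph:

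- Demographic and baseline characteristics: "By TEW-7197 sequence, descriptive statistics (number of subjects, mean, standard deviation, range, minimum, median, maximum) were tabulated for demographic information".
- Pharmacokinetic analysis: "Descriptive statistics were presented for mean, standard deviation and CV% by treatment (fed/fasting"), followed by a 90% confidence interval for the difference between treatments.
- Safety evaluation, adverse events and adverse drug reactions: "percentage and number of events were presented according to SOC and PT by dose group and treatment", then a further set of tables by severity, then "Chi-square test or McNemar's test was used to evaluate a statistical significance between treatments".
- Safety evaluation, measured safety items: "For vital signs, physical examination, 12-lead ECG, echocardiography and each item of clinical laboratory evaluations, descriptive statistics" are listed, and these "standard deviation, minimum, median, maximum and change from baseline (difference, change rate)) were tabulated by each measurement time". The sentence closes with "and for categorical data, frequency and percentage were tabulated. Concomitant medication was presented with lists".

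So the continuous summaries of the measured safety items name measurement time, and their categorical summaries name no grouping.

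**The concern.** In a cross-over every subject is planned to contribute to both conditions, so a table indexed by time alone does not say which condition a value belongs to. The author names the design factor for the pharmacokinetic summaries and for adverse-event incidence but not here, and that contrast invites the reading that the factor was dropped.

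If the tables were built that way, a reader could not see whether ECG, laboratory or vital-sign values moved differently after dosing with food and without. Adverse-event incidence by treatment would not replace that display, because it counts reported events and does not show shifts in measured values. Safety and tolerability stand beside pharmacokinetics in the title, so the loss would touch a stated aim. Change from baseline has a related gap: the text does not say which value serves as baseline in each period.

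**Working it through.** The SAP gives no figure on this point to reproduce. The check compares wording and then asks what each possible layout would show.

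**Step 1. Which outputs name treatment?**

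| Output | Grouping named |
|---|---|
| Demographics | sequence |
| PK descriptive statistics | dose group; treatment (fed/fasting) |
| PK 90% confidence interval | between treatments |
| AE/ADR incidence | SOC and PT, dose group, treatment |
| AE/ADR severity | SOC and PT, severity |
| Test after the AE/ADR tables | between treatments |
| Measured safety items, continuous | measurement time |
| Measured safety items, categorical | none |

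Treatment is named 4 times in the statistical text: twice for pharmacokinetics, once for adverse-event incidence and once for the test. From the start of the sentence on vital signs to the end of the section, treatment, period, sequence, fed and fasting are named 0 times. The sentence covers 5 classes of measure. The observation about the wording is therefore correct.

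**Step 2. Does the omission single out these five classes?** No. The severity tables also leave treatment out, although the incidence tables just before them include it. Other phrases are loose too. Outputs are grouped by dose group although the title gives one dose, 200 mg, and sex is listed as a demographic item in a study of male subjects. This pattern fits generic, shortened drafting.

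**Step 3. What would each layout show?** For a row that combines conditions,

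row mean = w × fed mean + (1 − w) × fasting mean, with 0 < w < 1.

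That is one reported value for two unknown condition means, so the contrast cannot be recovered. Whether w lies strictly between 0 and 1 depends on the layout. The demographic paragraph compares sequences with two-sample tests, which implies two sequences; I take two periods to go with them.

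- Time only, periods pooled: 0 < w < 1, conditions mixed.
- Time within period, sequences merged: 0 < w < 1, conditions mixed.
- Time within period, by sequence: w is 0 or 1, conditions separate.
- Time within treatment: w is 0 or 1, conditions separate.

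The SAP wording is compatible with all four. The loss arises under the first two, and nothing in the text selects them.

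**Step 4. What depends on these tables?** The 90% confidence interval uses log-transformed Cmax and AUCt. The between-treatment test follows the adverse-event tables. No test, margin or decision rule in the text uses the summaries of measured safety items.

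**The case for a change.** The strongest case for a change is that the omission is real, no other sentence fills it, and filling it is cheap. The break in the source table falls inside the list of statistics, before the grouping phrase, so the phrase is complete as printed. Reading measurement time as time within period is not enough on its own, because within one period one sequence is fed and the other fasting. Dose group cannot separate the conditions, since one dose is given under both. A single added phrase would remove all doubt, at the price of one extra column set for items measured in both periods.

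The textual part of this stands. The consequence does not, because it needs a further step: that the analysts of a study designed to compare fed with fasting would apply neither a treatment split nor a sequence split. The SAP does not say so.

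The reach of the argument is also uncertain. The assessment schedule is not in the supplied text, so five classes is an upper limit on what could be split; an item measured once per study cannot be. The text is in the past tense, so the tables may already exist. If they are split by condition, the added phrase would change nothing.

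**Conclusion.** No change to the plan is needed. The SAP leaves unstated whether the summaries of the five classes of measured safety items, and the adverse-event severity tables, are shown by fed and fasting condition. This is missing detail in a synopsis-length text, of a kind that analysts of a fed/fasting cross-over fill in as a matter of course. It is not an instruction to pool.

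The size is one unstated grouping factor in descriptive tables. No estimate, interval, test or conclusion changes, and no bias can be calculated or is claimed. The unstated baseline for each period is a gap of the same minor kind and adds no weight.

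This rests on two assumptions: that the analysts lay out these tables by condition, directly or through sequence and period, and that no decision outside the supplied text depends on them. If the tables did turn out to merge the conditions, a descriptive display would be lost for items measured in both periods, while the pharmacokinetic comparison and the adverse-event comparison would stand as they are.
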